2. LIST OF ABBREVIATIONS

Abbreviation	Definition
AE	adverse event
AEM	adverse event monitoring
BOR	best overall response
CI	confidence interval
CR	complete response
CRFs	Case report forms
CSA	clinical study agreement
CRP	C-reactive protein
DCF	data clarification form
DCTs	Data collection tools
eCRF	electronic case report form
eGFR	estimated glomerular filtration rate
ECOG	Eastern Cooperative Oncology Group
EDC	electronic data capture
FAS	Full analysis set
HR	hazard ratio
IMDC	International Metastatic RCC Database Consortium
IEC	independent ethics committee
irAE	immune-related adverse event
IRB	Institutional Review Board
JUA	Japanese Urological Association
mRCC	metastatic renal cell carcinoma

PFIZER CONFIDENTIAL

CT24-WI-GL02-RF02 4.0 Non-Interventional Study Protocol Template For Secondary Data Collection Study 01-Jun-2022

NIS	non-interventional study
NE	not Evaluable
NI	non-interventional
OS	Overall survival
ORR	objective response rate
PR	partial response
PD	progressive disease
PD-L1	anti-programmed death ligand 1
PFS	progression-free survival
RCC	renal cell carcinoma
RECIST	Response Evaluation Criteria in Solid Tumors
SAP	Statistical Analysis Plan
SD	stable disease
TNM	tumor-node-metastasis
TKI	tyrosine kinase inhibitor
TTD	time to treatment discontinuation
YRR	your reporting responsibilities

PFIZER CONFIDENTIAL

CT24-WI-GL02-RF02 4.0 Non-Interventional Study Protocol Template For Secondary Data Collection Study 01-Jun-2022

3. RESPONSIBLE PARTIES

Principal Investigator(s) of the Protocol

The implementation structure of this study will be prepared in Annex 1.

4. ABSTRACT

Not applicable

5. AMENDMENTS AND UPDATES

Amendment number	Date	Protocol section(s) changed	Summary of amendment(s)	Reason
1.1	14 Oct 2022	6. MILESTONES 9.8. Quality control 10.2.4. Disclosing study findings to patients ANNEX 1. LIST OF STAND ALONE DOCUMENTS	6. added anticipated study start date 9.8. added data monitoring procedure 10.2.4. added plans to communicate study results to participants ANNEX 1. changed the name of the site	6. to clarify study period 9.8. to clarify data monitoring procedure 10.2.4. to clarify how to deal with study results including incidental or secondary findings ANNEX 1. to correct typos
1.2	31 Oct 2022	9.8. Quality control	9.8. added the affiliation of the data manager	9.8. to clarify who is in charge of data monitoring

PFIZER CONFIDENTIAL

CT24-WI-GL02-RF02 4.0 Non-Interventional Study Protocol Template For Secondary Data Collection Study 01-Jun-2022

6. MILESTONES

Milestone	Planned date
Study start date	Date of approval at each site
Start of data collection	15 December 2022
End of data collection	30 April 2023
Final study report	30 November 2023

7. RATIONALE AND BACKGROUND

In Japan, nearly 30,000 patients were diagnosed with renal cancer in 2018, and the number of patients has increased annually since the 1980s ¹⁾. The 5-year relative survival rate for renal/urinary tract cancer (excluding bladder cancer) was 68.6% between 2009 and 2011. In 2020, Nine Thousand Seven Hundred Twelve deaths occurred, with a mortality rate of 7.6 per 100,000 persons. Although the incidence of renal cell carcinoma (RCC) in Japan is lower than that in other modernized countries, it continues to increase ^{1,2)}.

Recently, the immunotherapeutic approaches have demonstrated clinical efficacy in several types of cancer, and certain immune checkpoint inhibitors have been approved for the treatment of RCC. ³⁻⁷⁾ One of these immune checkpoint inhibitors is avelumab, an anti-programmed death ligand 1 (PD-L1) antibody. In December 2019, avelumab plus axitinib combination therapy was approved in Japan as the first-line treatment for unresectable or mRCC. ⁴⁾ This is the first therapy approved in Japan that has combined an immuno-oncology drug with a tyrosine kinase inhibitor (TKI) in order to treat patients with mRCC. The recent Japanese Urological Association (JUA) guidelines for renal cancer recommended the combination of avelumab and axitinib as first-line therapy for RCC [Grade B]. ⁸⁾

The Phase 3 JAVELIN Renal 101 trial compared the combination of avelumab plus axitinib with sunitinib monotherapy in previously untreated patients with advanced RCC. ⁴⁾ The results showed a statistically significantly longer median progression-free survival (PFS) in those treated with the combination therapy (13.8 months; 95% confidence interval [CI]: 11.1–inestimable) as compared with sunitinib (7.2 months; 95% CI: 5.7–9.7) as well as a hazard ratio (HR) of 0.61 for disease progression or death (95% CI: 0.47–0.79; $P <0.001$). These findings were sustained even after a minimum follow-up of 13 months (HR: 0.62; 95% CI: 0.49–0.78; one-sided $P <0.0001$), ⁹⁾ and similar results were obtained in subgroup analyses within each age category (<65 years, 65–74 years, \geq 75 years), including the population aged 75 years and over. ¹⁰⁾

Although several clinical trials have focused on avelumab plus axitinib regimens in the treatment of mRCC, there is limited evidence in real-world settings in Japan. Moreover, because more than 1-year follow-up period is required to assess the real-world effectiveness of this combination therapy, such as in regard to PFS, we planned a series of 3 studies with different long-term follow-up periods. As the first of these studies, J-DART1-B9991043, was conducted to evaluate the treatment outcomes over the course of 1-year in Japanese patients with mRCC who were treated with avelumab plus axitinib as first-line therapy in a real-world clinical setting (NCT05012865). This second study, J-DART2-B9991052, is being conducted in order to describe the demographic and characteristics of the patients as well as the treatment outcomes over the course of more than 2-years of follow-up in Japanese

patients with mRCC who were treated with avelumab plus axitinib as first-line therapy in a real-world clinical setting.

8. RESEARCH QUESTION AND OBJECTIVES

8.1. Primary objective

- To describe the demographic and clinical characteristics of Japanese patients with mRCC treated with avelumab plus axitinib as first-line therapy in a real-world setting.

8.2. Secondary objectives

- To evaluate the treatment outcomes of avelumab plus axitinib as first-line therapy for patients with mRCC in a real-world setting, as determined by the following endpoints:
 - Real-world PFS.
 - Overall survival (OS).
 - Objective response rate (ORR).
 - Best overall response (BOR) for primary lesions.
 - Time to treatment discontinuation (TTD) of avelumab plus axitinib as first-line therapy.
- To describe the treatment patterns for avelumab plus axitinib as first-line therapy in a real-world setting.
- To describe the clinical use of corticosteroids for immune-related adverse events (irAEs) occurring during the course of administering avelumab plus axitinib combination therapy.
- To describe the pre-treatment and treatment of infusion-related reactions caused by avelumab.
- To describe the subsequent treatment of avelumab plus axitinib combination therapy.

CCI

9. RESEARCH METHODS

9.1. Study design

This study is a multicenter, NI, retrospective, medical chart review of patients with mRCC who were treated with avelumab plus axitinib as first-line therapy in Japan between 20 December 2019 and 17 October 2022.

The source population comprises patients who initiated avelumab plus axitinib as first-line therapy between 20 December 2019 and 17 October 2022.

9.2. Setting

This retrospective chart review will evaluate patient data derived from patient's existing medical records from the enrolled patients. All decisions regarding the clinical management and treatment of the patients are made by the investigator as part of standard care in a real-world setting and are not contingent upon the patient's participation in the study. Data will be collected at each study site (if available).

PFIZER CONFIDENTIAL

CT24-WI-GL02-RF02 4.0 Non-Interventional Study Protocol Template For Secondary Data Collection Study 01-Jun-2022

The study period is from 20 December 2019 to 31 October 2022. Patients with index date between 20 December 2019 and 17 October 2022 will be enrolled in this study. To ensure a 2 weeks follow up period, patients with an index date between 20 December 2019 and 17 October 2022 will be included in this study. The period of 2 weeks is determined based on the dosing interval for avelumab, in consideration of the fact that the start times of administration for avelumab and axitinib may differ.

- Index date: The date of first prescription of avelumab plus axitinib combination therapy.
- Observation period: Patients will be followed from the index date to 31 October 2022.

9.2.1. Inclusion criteria

Patients must meet all of the following inclusion criteria to be eligible for inclusion in the study:

- 1) Diagnoses of mRCC based on the General Rule for Clinical and Pathological Studies on RCC (Fifth Edition) before receiving avelumab plus axitinib as first-line therapy. Patients with mRCC who have unresectable disease, either unresectable locally advanced or metastatic disease.
- 2) Age over 18 years at the time of the first administration of avelumab plus axitinib as first-line therapy for mRCC (baseline).
- 3) Index date from 20 December 2019 to 17 October 2022.

9.2.2. Exclusion criteria

Patients meeting any of the following criteria will not be included in the study:

- 1) Patients participating in a prospective interventional clinical trial assessing an investigational product during the observation period.
- 2) Patients (or a patient's legally representative) refusing to provide patient data during the consent process.

9.3. Variables

Only data available from the treating physician's routine clinical assessments as per local standard of care will be collected. Variables and data sources are described in [Table 1](#). Detailed definitions will be included in the Statistical Analysis Plan (SAP).

Table 1. Variables in this study

Variable	Role	Data source(s)	Operational definition
Patient characteristics	Baseline characteristics, sub-group identifiers	Patient medical records	Patient characteristics at baseline, including the most recent data prior to initial treatment with avelumab plus axitinib: age, sex, height, weight, body mass index, smoking history, comorbidities, concomitant use of drugs, Eastern Cooperative Oncology Group (ECOG) performance status, pathological diagnosis (Fuhrman grade, TNM classification, histological type sarcomatoid component), the number of metastatic organs and the site of metastasis, the presence or absence of

PFIZER CONFIDENTIAL

CT24-WI-GL02-RF02 4.0 Non-Interventional Study Protocol Template For Secondary Data Collection Study 01-Jun-2022

			
nephrectomy, laboratory data (C-reactive protein (CRP), estimated glomerular filtration rate (eGFR), proteinuria), and International Metastatic RCC Database Consortium (IMDC) risk score
 
 - <1 year from time of diagnosis to systemic therapy - Karnofsky Performance Status <80% - Hemoglobin < lower limit of normal - Corrected calcium > upper limit of normal - Neutrophils > upper limit of normal - Platelets > upper limit of normal)
Avelumab plus axitinib treatment patterns	Exposure, outcome, sub-group identifier	Patient medical records	Start and end date of avelumab plus axitinib as first-line therapy.
Management of AE	Exposure, outcome, sub-group identifier	Patient medical records	Corticosteroid treatment for irAEs occurring during treatment with avelumab plus axitinib (drug, dose), the presence or absence of pre-medication and treatment for infusion-related reactions.
Subsequent treatment patterns	Exposure, outcome, sub-group identifier	Patient medical records	Subsequent treatment (drug name and duration of use for second-line therapy).
Clinical outcomes	Outcome	Patient medical records	
BOR, assessment of disease progression, real-world PFS, OS, ORR, TTD.
 
For the patients not nephrectomized at baseline: BOR for the primary lesion, the date of nephrectomy after administration of avelumab plus axitinib.

9.3.1. Definition of clinical outcome measures

Real-world progression-free survival (PFS)

Real-world PFS is defined as the time from the start of treatment with avelumab plus axitinib to the date of first disease progression (as clinically assessed by a local investigator based on a radiology assessment, laboratory evidence, pathological data, and/or other assessments) or death due to any cause, which ever came first. If there are no clinical records of death or disease progression, patients will be censored at the date of initiation of the next line of therapy for those undertaking 2 or more lines of therapy based on the details in their medical records or at their last visit date during the study period for those undergoing only first line of therapy. However, if the nephrectomy is performed earlier than the above date, the data is to be treated as censored at the date of nephrectomy.

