9.5. Study size

This descriptive study aims to describe the demographic and baseline characteristics for patients treated with avelumab plus axitinib as first-line therapy for mRCC, rather than testing any predefined hypothesis. Since all analyses are descriptive, sample size calculations are not applicable.

The expected number of patients is approximately 150 patients in total. However, this number should be considered flexible.

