### **5.1 EFFICACY/EFFECTIVENESS ENDPOINT(S)**

<Derivation of time-to-event variables>

Item	Derivation method
Real-world progression-free survival (PFS)	Defined as the period from the start date of avelumab plus axitinib combination therapy to

PFIZER CONFIDENTIAL

	
the date of first disease progression (clinical evaluation based on radiographic, clinical, and pathological examinations, as well as other evaluations by the principal investigator or co-investigator) or death from any cause, whichever occurs earlier. If there is no clinical record of death or disease progression, the following dates will be used for censoring, based on medical records:
 
 
(1) If first-line therapy is ongoing, the final progression-free confirmation date or the date of the last hospital visit, whichever is earlier, will be used for censoring.
 
(2) If second-line therapy has not been initiated after the end of first-line therapy, the final progression-free confirmation date or the date of the last hospital visit, whichever is earlier, will be used for censoring.
 
(3) If second-line therapy has been initiated, the date of initiating the second-line therapy will be used for censoring.
 
(4) If nephrectomy has been performed, the date of nephrectomy will be used for censoring.
 

Reasons for real-world PFS events	
Reasons for real-world PFS events are defined as follows:
 
"Disease progression after the initiation of avelumab plus axitinib combination therapy" will be selected if there was disease progression after starting avelumab plus axitinib combination therapy.
 
"Death" will be selected if the patient has died.

Reasons for censoring real-world PFS	
Reasons for censoring real-world PFS are defined as follows:
 
"No disease progression during or after first-line therapy" will be selected if first-line therapy is ongoing or if second-line therapy has not been initiated after the end of first-line therapy.
 
"Second-line therapy started" will be selected if second-line therapy has been initiated.
 
"Nephrectomy performed" will be selected if nephrectomy has been performed.

Overall survival (OS)	
Defined as the period from the initiation of avelumab plus axitinib combination therapy to the date of death from any cause. If there is no

PFIZER CONFIDENTIAL

CT24-WI-GL03-RF03 2.0 *Non-Interventional Statistical Analysis Plan For Secondary Data Collection*  

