### **Analysis of secondary objectives**

#### **7.2.2.2 Real-world progression-free survival**

Source : Efficacy analysis set  
 population  
 Endpoint : Real-world PFS  
 Analysis content : For the endpoint, the median and its 95% confidence interval will be calculated using the Kaplan–Meier method. In addition, the Kaplan–Meier curve will be plotted, and the PFS rate for every 12 months and its 95% confidence interval will be calculated. Greenwood’s formula will be used to calculate the confidence interval for the PFS rate. In addition, the number of event-onset cases and the number of censored cases will be presented. A frequency table (number of cases, percentage (%)) will be created, considering the reasons for the event and reasons for censoring. In order to evaluate the observation period, the median observation period and its 95% confidence interval will be calculated by estimating the reverse Kaplan-Meier curve in which censoring patients are regarded as patients with events and patients with events are regarded as censoring patients.

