#### **【Division of categorical variables】**

Factor	Category
Reasons for the event	Disease progression after the start of avelumab plus axitinib; Death
Reasons for the censoring	No disease progression during or after first-line therapy; second-line therapy started; nephrectomy performed

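### Real-world PFS is censored at nephrectomy with no check that surgery is unrelated to prognosis, and the SAP wording lets the rule depend on what is recorded after surgery

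*Protocol*

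**What the plan says.** Protocol 9.3.1 defines real-world PFS as time to first progression or death. It then gives censoring dates for patients with neither on record, and adds that "if the nephrectomy is performed earlier than the above date, the data is to be treated as censored at the date of nephrectomy".

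SAP 5.1 opens its censoring list with a condition: "If there is no clinical record of death or disease progression, the following dates will be used for censoring". Rule (4) in that list reads: "If nephrectomy has been performed, the date of nephrectomy will be used for censoring".

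SAP 7.2.2.2 takes the median from Kaplan-Meier, and "the PFS rate for every 12 months and its 95% confidence interval will be calculated", using Greenwood's formula. The readable text deals with nephrectomy censoring only by counting it among the reasons for censoring: "No disease progression during or after first-line therapy; second-line therapy started; nephrectomy performed".

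Protocol Table 1 collects, for patients not nephrectomized at baseline, "the date of nephrectomy after administration of avelumab plus axitinib". Neither OS nor TTD is censored at nephrectomy.

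**The concern.** Kaplan-Meier lets the patients still at risk stand in for those who were censored. For nephrectomy, that means assuming an operated patient would have progressed at the same rate as one not operated on. A clinical decision such as surgery may well depend on how the patient is doing, and the documents neither state nor defend the assumption.

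The second difficulty is the wording. Because rule (4) sits under a condition about recorded events, two programmers could apply it differently:

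- **Censor all.** Every patient operated on before progression is censored at surgery, whatever happens later.
- **Literal.** An operated patient who later progresses or dies counts as an event on that later date. Only operated patients with no recorded event are cut back to surgery.

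The protocol's phrase about the date above does not settle which is meant. It could refer to the censoring date alone, or to the progression and death dates as well.

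At stake are the median and the 12- and 24-month rates of one of the study's treatment outcomes. The 24-month figure matters most, since the study was set up for follow-up beyond two years. The reverse Kaplan-Meier follow-up estimate for PFS also inherits whichever rule is used.

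**Working it through.** The plan gives no power or event figure to reproduce: "sample size calculations are not applicable". The check is therefore a simulation of direction and rough size.

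**Inputs from the documents**
- Cohort size: "The expected number of patients is approximately 150 patients in total".
- Potential follow-up in the efficacy set, with the SAP's 30.4375 days per month. Shortest: 29 April to 31 October 2022, 185/30.4375 = 6.1 months. Longest: 20 December 2019 to 31 October 2022, 1046/30.4375 = 34.4 months.
- Median PFS of 13.8 months, from the phase 3 trial cited in Protocol 7, used only to set the scale.

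**Assumptions not in the documents**
- Half the patients have good and half poor prognosis, with a good-to-poor hazard ratio h of 0.5 or 0.3.
- Follow-up is uniform over the range above.
- Surgery takes place at 4 to 12 months in progression-free patients and has no effect on progression.
- 10% of the cohort is operated on.

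**Model.** S(t) = 0.5·exp(−λp·t) + 0.5·exp(−h·λp·t), with λp solved so that S(13.8) = 0.5.
- h = 0.5: λp = 0.0697, so S(24) = 0.5·exp(−1.674) + 0.5·exp(−0.837) = 31.0%.
- h = 0.3: λp = 0.0868, so S(24) = 0.5·exp(−2.083) + 0.5·exp(−0.625) = 33.0%.

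Kaplan-Meier was run on 600,000 simulated patients per scenario in three ways: following patients through surgery, censoring all at surgery, and applying the literal reading.

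**24-month PFS in %, 10% operated (h = 0.5 / h = 0.3)**

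| Who is operated on | Followed through | Censor all | Difference | Literal | Difference |
|---|---|---|---|---|---|
| Good prognosis | 31.0 / 33.0 | 29.6 / 31.0 | −1.4 / −2.0 | 27.6 / 29.2 | −3.4 / −3.8 |
| Unrelated to prognosis | 31.1 / 32.9 | 31.1 / 32.9 | 0 / 0 | 28.4 / 30.1 | −2.7 / −2.8 |
| Poor prognosis | 31.1 / 32.9 | 32.8 / 36.1 | +1.7 / +3.2 | 29.2 / 31.6 | −1.9 / −1.3 |

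**Medians.** Followed through surgery, the median is 13.8 months. Censoring all gives 13.5 / 13.3 (good), 13.8 / 13.8 (unrelated) and 14.3 / 14.8 (poor). The literal reading gives 13.2 / 13.2 even when surgery is unrelated to prognosis.

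**Other shares operated.** With good-prognosis surgery and all censored, the 24-month shortfall runs from 0.6 / 0.9 points at 5% operated to 3.3 / 4.9 points at 20%.

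**Second set of assumptions.** 55% responders with median PFS 24 months, the rest 7 months; surgery at 4 to 14 months; follow-up 6 to 34.4 months. True S(24) = 0.55·0.5 + 0.45·2^(−24/7) = 31.7%. With 10% operated and all censored, the estimate is 1.6 to 1.8 points low if only responders have surgery, unchanged if surgery is unrelated to prognosis, and 3.7 points high if only non-responders have it (with the whole cohort open to surgery). The literal reading with unrelated surgery is about 3 points low.

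**Why the literal reading pulls PFS down.** It keeps every event after surgery but drops the event-free time after surgery of patients who have no event. The hazard then has its full numerator over a reduced denominator.

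**Sampling error.** At N = 150 the average 95% half-width (1.96 times the Greenwood standard error) is 8.2 points at 12 months and 9.3 points at 24 months.

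**The case against.** The tempting reading is that real-world PFS is understated, because a patient must be progression-free to be censored at surgery and so those removed must be the ones doing best. The documents do not support it. Everyone still at risk at that moment is also progression-free, so the comparison turns on why some were chosen for surgery, and nothing in either document says. Under uniform censoring the sign reverses if patients doing badly are selected.

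Censoring at a major local treatment can also be a deliberate choice, since the objective concerns outcomes of avelumab plus axitinib. If surgery itself delays progression, following patients through it brings that benefit into the estimate, and the resulting gap is a change of target rather than a bias. This stands, and is why the current definition should stay. It does not remove the need for independent censoring, and no such target is stated.

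The consequences are limited. PFS is a secondary outcome in a descriptive study without a hypothesis test, the number censored at surgery will be reported, and most of the shifts above lie within sampling error. That also stands. But the confidence interval does not cover this kind of error, and a count of censored patients does not show how they fared.

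Finally, parts of the analysis text are redacted, and a follow-through analysis may be there. Nothing is counted as missing on that account; the point concerns only what can be read.

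**Conclusion.** The concern holds as one of unknown direction and modest size. Real-world PFS depends on an unstated assumption about surgery, and no readable analysis shows how much that matters. With 10% operated and uniform censoring, the assumed scenarios run from about 2 points low to about 4 points high at 24 months, with no shift when surgery is unrelated to prognosis. All of this rests on the assumed share operated and prognostic mix.

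The wording problem is firmer. If rule (4) is applied literally, PFS is low in all three selection scenarios, by about 3 points at 10% operated when surgery is unrelated to prognosis. A claim that uniform selection makes the rule harmless is therefore true only if all operated patients are censored alike.

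This is a worthwhile, inexpensive improvement. It does not show that the planned PFS estimate is wrong.

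**What to change.** 1. Keep the current definition, and state in SAP 5.1 that a patient operated on before progression is censored at nephrectomy whatever is recorded afterwards, so that all operated patients are treated alike. Bring the wording of Protocol 9.3.1 and SAP 5.1 into line.
2. Add to SAP 5.1 and 7.2.2.2 a sensitivity version of real-world PFS that ignores nephrectomy and follows each patient to progression, death, second-line start or last progression-free confirmation.
3. Report the median and the 12- and 24-month rates of both versions side by side.

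The cost is one sentence of definition and one more Kaplan-Meier run on dates the study already collects. The small downside is that the second estimate describes drug plus surgery where surgery was done, and it should be labelled so. The second curve shows the difference whichever way it goes, and the ambiguity in rule (4) does not affect it.
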